13.2 Randomization/Stratification

Patients will be randomized by the study statistician at Northwestern University. Randomization will be carried out among consented patients meeting the Screen 2 eligibility criteria at each study site with a 2:1 ratio for simvastatin and placebo assignment.

13.3 Accrual and Feasibility

Sample size: Intervention = 30 (20:10) randomized sample; after 20% drop out = 24 (16:8) analytic sample. The expected accrual rate is 1-2 participants per month across four study sites, and the planned recruitment duration is 24 months. We anticipate that all evaluable participants will have completed all study procedures within three years. Power and precision arguments are provided below.

13.4 Primary Objective, Endpoint(s), Analysis Plan

The primary outcome for this study is change from baseline (Study Visit 1) at 6 months of peak bicarbonate concentration as measured by ePFT. For the primary endpoint, we will consider differences D(T) and D(P) for D=After-Before, for Treatment and Placebo (Control) groups respectively. Then we will use a nonparametric two-sample Wilcoxon-Mann-Whitney test to address the hypothesis H0: mean [D (T)] =mean [D (P)] versus H1: mean[D(T)] > mean[D(P)], and report a one-sided p-value, as presented in Table 3. If p<0.05 we will consider this to be evidence of activity in the simvastatin group.

Table 3. Numeric Results for Mann-Whitney Test (Uniform Distribution)									
Power	N1	N2	Ratio	Alpha	Beta	Mean1	Mean2	S1	S2
0.82	16	8	0.5	0.05	0.18	25	10	13	13
Null Hypothesis: Mean1=Mean2. Alternative Hypothesis: Mean1>Mean2. The standard deviations were assumed to be equal at 13 mEq/L.									

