13. STATISTICAL CONSIDERATIONS

13.1 Study Design/Description

This is a phase II randomized, double-blinded, placebo-controlled trial of statin to evaluate the impact of statin treatment on pancreatic function and inflammation implicated in pancreatic carcinogenesis in patients with recurrent acute pancreatitis. The primary objective of this study will be to demonstrate that statins will improve pancreatic function in high-risk patients, as defined by those with two or more episodes of acute pancreatitis in the past 12 months.

The primary outcome for this study is change from baseline (Study Visit 1) at 6 months of *peak bicarbonate concentration* as measured by *ePFT*. Sample size calculations follow from computations PASS 11 (www.ncss.com). Means and standard deviations of peak bicarbonate concentrations are derived from the literature on the validity and utility of *ePFT* for diagnosis of chronic pancreatitis [56, 57]. We expect baseline peak bicarbonate levels to be 60 mEq/L in these patients with recurrent pancreatitis, with a standard deviation of 13 mEq/L. We expect the peak bicarbonate levels to increase in both simvastatin and placebo groups as the groups recover from the acute pancreatitis event, with the simvastatin group showing a greater increase to full recovery compared to the placebo group. An analytic sample size of 24 (after 20% drop out) will have 82% power to detect a statistically significant one-sided difference of 15 mEq/L (25 vs. 10 mEq/L) at an alpha level of 0.05. The anticipated changes are well within the range of

peak bicarbonate levels of patients with mild to severe pancreatitis [56, 57] whose median peak bicarbonate levels range from 40 mEq/L to 100 mEq/L.

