13.5 Secondary Objectives, Endpoints, Analysis Plans

For secondary endpoints, we will consider D(T) and D(P) as well as percent change relative to baseline as well, namely, D (T)/B (T) and D (P)/B (P). For all secondary variables, we will use descriptive statistics and graphics at 3 months and at 6 months, as well as study random effects regression trends along the timeline Baseline → 3 months → 6 months for further hypotheses generation. In particular, we will look into cytokines, chemokines, and adhesion molecules and quality of life scores from the QLQ-C30 and QLQ-PAN28(CP) assessment after possible log-transformation of continuous data. In particular, we will be interested in the relation between a) pairs of secondary variables and differences D=After-Before in pairs of secondary variables in the Treatment group, b) same as a) but in the control group, c) comparing pairwise changes between the Treatment and the Control groups, and d) relationship of secondary outcomes with recurrent pancreatitis. In this way, we will be able to study co-dependence among various secondary variables and their possible relationship with recurrent pancreatitis. We will thus fit various regression models, estimate relevant parameters (e.g., intercept, slope) and explore the apparent magnitudes of change in these parameters in the treatment and the control group.

Analyses will be performed with Stata software. All analyses will be conducted on an intention to treat basis (all randomized participants will be included in the assigned group) and will begin with univariate cross-sectional statistics for profiling the study population and bivariate tabulations as a preliminary step to possible model building. We will not control for overall Type I error due to small number of

observations and the preliminary nature of the study.

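### The primary test in Section 13.4 is valid but ignores baseline bicarbonate; adjusting for the Screen 2 value would stop chance baseline imbalance from moving the verdict

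*Combined protocol and SAP*

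**What the plan says.** For the primary endpoint, Section 13.4 states "we will consider differences D(T) and D(P) for D=After-Before", and continues: "Then we will use a nonparametric two-sample Wilcoxon-Mann-Whitney test to address the hypothesis". A one-sided p below 0.05 is taken as showing activity. No baseline covariate and no adjusted sensitivity analysis is named. The note to Table 3 adds: "The standard deviations were assumed to be equal at 13 mEq/L".

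Section 13.1 gives the planning figures: "We expect baseline peak bicarbonate levels to be 60 mEq/L in these patients with recurrent pancreatitis, with a standard deviation of 13 mEq/L"; "Means and standard deviations of peak bicarbonate concentrations are derived from the literature"; and "An analytic sample size of 24 (after 20% drop out) will have 82% power" for a difference of 15 mEq/L (25 against 10).

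Section 13.2 describes allocation: "Randomization will be carried out among consented patients meeting the Screen 2 eligibility criteria at each study site with a 2:1 ratio". It mentions no balancing on baseline bicarbonate. The regression models in Section 13.5 serve the secondary endpoints: "For all secondary variables, we will use descriptive statistics and graphics at 3 months and at 6 months", followed by random-effects trends meant to generate hypotheses. Section 7.2.3 takes the baseline ePFT at Screen 2, before randomisation, so the covariate is already collected.

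**The concern.** Subtracting the baseline is the same as assuming that Month-6 bicarbonate rises by 1 mEq/L for every 1 mEq/L at baseline. If the true slope is below 1, patients who start low tend to rise more whatever they are given. With 16 against 8 patients and nothing in Section 13.2 to balance the arms on bicarbonate, sizeable chance differences at baseline are common, and part of each one passes into the treatment contrast.

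One p-value decides the trial, and its readers will have the baseline table beside it. If simvastatin starts lower and p is below 0.05, they cannot tell activity from regression to the mean. If simvastatin starts higher, a real effect may be missed.

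**Working it through.** **1. Inputs.** From Sections 13.1 to 13.4: 16 against 8 analysed, difference 15, baseline SD 13, SD 13 in Table 3, one-sided 0.05. Not in the documents, so treated as assumptions with a range: the Month-6 SD and the correlation r between baseline and Month 6.

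**2. The plan's power.** SE = 13 × √(1/16 + 1/8) = 5.63. Noncentrality = 15 / 5.63 = 2.66 with 22 df. Power from the noncentral t, with efficiency factor 1 for the uniform distribution named in Table 3, is 0.825 against the stated 0.82. The exact test rejects at U ≥ 92 and has size 0.0463. Simulated with that cutoff, its power is 0.79 with normal errors and 0.76 with uniform errors. The comparisons below use normal errors unless stated.

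**3. Chance imbalance.** The baseline SD is also 13, so the difference in baseline means has SD 5.63. P(|difference| > 5) = 2 × (1 − Φ(5/5.63)) = 0.374, or 0.187 in each direction.

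**4. Effect on the contrast.** If simvastatin starts lower by Δ, the expected change-score contrast is the true effect plus (1 − slope) × Δ.

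**5. What slope do the plan's figures imply?** Table 3's SD can be read in two ways.
- *Reading A: 13 is the SD of change.* With Month-6 SD s, 13² + s² − 2r × 13 × s = 169 gives r = s/26, and slope = r × s/13 = s²/338.
- *Reading B: 13 is the SD of the levels*, as the wording of Section 13.1 suggests. With SD 13 at both visits the slope equals r, which is below 1 for any r below 1.

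**6. Simulation, Reading A** (120,000 trials per setting). Adjusted means ANCOVA on baseline with a re-randomisation p-value from 999 draws.

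| Month-6 SD | Slope | Shift per 5 mEq/L | Power: Mann-Whitney | Power: t-test on change | Power: adjusted | No effect, simvastatin >5 lower: MW / adjusted | Effect 15, simvastatin >5 higher: MW / adjusted |
|---|---|---|---|---|---|---|---|
| 10 | 0.30 | 3.5 | 0.793 | 0.825 | 0.970 | 0.179 / 0.052 | 0.438 / 0.961 |
| 13 | 0.50 | 2.5 | 0.791 | 0.825 | 0.893 | 0.135 / 0.051 | 0.564 / 0.874 |
| 15 | 0.67 | 1.7 | 0.792 | 0.825 | 0.843 | 0.099 / 0.051 | 0.654 / 0.827 |
| 16 | 0.76 | 1.2 | 0.793 | 0.827 | 0.827 | 0.083 / 0.048 | 0.693 / 0.807 |
| 17 | 0.86 | 0.7 | 0.793 | 0.826 | 0.814 | 0.069 / 0.050 | 0.730 / 0.791 |
| 18.4 | 1.00 | 0.0 | 0.792 | 0.825 | 0.806 | 0.044 / 0.048 | 0.791 / 0.786 |
| 20 | 1.18 | −0.9 | 0.792 | 0.825 | 0.816 | 0.026 / 0.050 | 0.857 / 0.796 |

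The value of adjustment itself is the adjusted column minus the t-test column: about +14, +7, +2, 0, −1, −2 and −1 points. From SD 16 upward, any remaining lead over Mann-Whitney comes from leaving the rank test.

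**7. Reading B.** r = 0.5 is the SD 13 row above.

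| r | Power: Mann-Whitney | Power: t-test on change | Power: adjusted | No effect, simvastatin >5 lower: MW / adjusted |
|---|---|---|---|---|
| 0.3 | 0.666 | 0.705 | 0.837 | 0.154 / 0.048 |
| 0.7 | 0.938 | 0.955 | 0.968 | 0.110 / 0.050 |
| 0.8 | 0.988 | 0.993 | 0.994 | 0.100 / 0.051 |

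**8. All baseline strata, no effect** (40,000 trials per setting). Mann-Whitney rejection when simvastatin starts more than 5 lower / within 5 / more than 5 higher: 12.7 / 3.5 / 0.5% at Month-6 SD 13 (overall 4.6%), and 7.9 / 4.2 / 1.9% at SD 16 (overall 4.5%).

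**9. Checks on the adjusted test.**
- Thirty patients in assumed 2:1 blocks of 3, with 4 + 2 random drop-outs and re-randomisation within blocks: size 0.051 to 0.053; power 0.885 / 0.815 / 0.800 at Month-6 SD 13 / 16 / 18.4.
- Level SD 13, r = 0.5 then 0.7, power Mann-Whitney / adjusted: t(3) errors 0.885 / 0.909, 0.979 / 0.958; lognormal errors 0.926 / 0.915, 0.982 / 0.952.
- Placebo residual SD 1.5 or 2 times larger, equal means: size 0.059 or 0.067 for Mann-Whitney, 0.069 or 0.083 adjusted.

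**The case against.** The best case for leaving the plan alone is that nothing is broken. Overall type I error is controlled, and the false positives in step 6 are offset by low rates where simvastatin starts higher, as step 8 shows. The same holds for power: at slope 0.5, Mann-Whitney has power 0.92 when simvastatin starts one SD of the imbalance lower, 0.83 with no imbalance and 0.66 when it starts that much higher. A rank test is a defensible choice with 8 placebo patients. The power gain depends on a slope the documents do not give, and on Reading A it vanishes from Month-6 SD 16 upward. ANCOVA tolerates unequal variances less well. Changing the decision rule is also delicate, because the study statistician is unblinded (Section 6.8) and manages the data (Section 12.1).

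All of this stands as fact, and it is why the point is an improvement. It does not remove the case for adjusting. An unknown slope favours estimating it over fixing it at 1, and on Reading A a slope of 1 needs a Month-6 SD of about 18.4, a figure the plan never gives. Offsetting errors over hypothetical trials do not help in reading the single trial that will be run. In the same slope-0.5 settings ANCOVA has power 0.89, 0.91 and 0.89. Adjustment added after the data are seen, by an unblinded statistician, would carry little weight.

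**Conclusion.** The concern holds as a recommended improvement, with medium confidence. The planned test is valid and its power statement reproduces. Its verdict nevertheless moves with chance baseline imbalance unless the slope is near 1: each 5 mEq/L of imbalance shifts the contrast by 2.5 mEq/L at Month-6 SD 13, by 1.2 at SD 16, and not at all at SD 18.4. Imbalance of more than 5 mEq/L in one direction or the other is expected in 37% of such trials.

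The main benefit of adjusting is a verdict that no longer depends on that accident. More power is a possible extra, large only if the Month-6 SD is about 13 or less (Reading A) or r is modest (Reading B). These sizes assume a baseline SD of 13, 16 against 8 analysed, normal errors and complete data in those analysed.

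**What to change.** Before Month-6 bicarbonate is linked to arm, and with that date documented, amend Section 13.4 along these lines:

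> Primary analysis: ANCOVA of Month-6 peak bicarbonate on arm and Screen 2 peak bicarbonate. The arm coefficient is the adjusted difference in change; it is the same whether level or change is the outcome. The one-sided p-value (0.05) comes from re-randomising arm labels under the allocation scheme actually used (2:1, with sites and blocks as set), with the ANCOVA arm coefficient as the statistic. The 90% CI is obtained by inverting the same test. Sensitivity analysis: Mann-Whitney test on After-Before. If the two disagree, the ANCOVA decides.

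In Section 13.1 and Table 3, state that the 82% refers to the unadjusted Mann-Whitney test on change. Add a figure for the new primary test: simulated power of about 0.80 to 0.97 for 15 mEq/L, with normal errors, change SD 13 and Month-6 SD between 10 and 20. The amendment should also say how missing Month-6 values are handled, since Section 13.6 expects 6 of 30 to drop out and Section 13.8 evaluates everyone randomised. That is a separate issue, not settled here.

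**Cost.** One amendment with DCP and IRB approval (Section 14.3); no new visits, samples or patients. Statistically:
- about 1 to 2 points of power against a t-test on change if the slope is near 1;
- about 1 to 3 points against Mann-Whitney in some heavy-tailed or skewed settings;
- size of 6.9 to 8.3% if placebo residuals are 1.5 to 2 times as variable.

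A lighter option keeps Mann-Whitney primary and prespecifies the ANCOVA as a sensitivity analysis. That leaves the decision rule unchanged, but also leaves the verdict open to the shift.

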13.5 Secondary Objectives, Endpoints, Analysis Plans

For secondary endpoints, we will consider D(T) and D(P) as well as percent change relative to baseline as well, namely, D (T)/B (T) and D (P)/B (P). For all secondary variables, we will use descriptive statistics and graphics at 3 months and at 6 months, as well as study random effects regression trends along the timeline Baseline → 3 months → 6 months for further hypotheses generation. In particular, we will look into cytokines, chemokines, and adhesion molecules and quality of life scores from the QLQ-C30 and QLQ-PAN28(CP) assessment after possible log-transformation of continuous data. In particular, we will be interested in the relation between a) pairs of secondary variables and differences D=After-Before in pairs of secondary variables in the Treatment group, b) same as a) but in the control group, c) comparing pairwise changes between the Treatment and the Control groups, and d) relationship of secondary outcomes with recurrent pancreatitis. In this way, we will be able to study co-dependence among various secondary variables and their possible relationship with recurrent pancreatitis. We will thus fit various regression models, estimate relevant parameters (e.g., intercept, slope) and explore the apparent magnitudes of change in these parameters in the treatment and the control group.

Analyses will be performed with Stata software. All analyses will be conducted on an intention to treat basis (all randomized participants will be included in the assigned group) and will begin with univariate cross-sectional statistics for profiling the study population and bivariate tabulations as a preliminary step to possible model building. We will not control for overall Type I error due to small number of

observations and the preliminary nature of the study.

13.6 Reporting and Exclusions

We anticipate some contamination from the simvastatin intervention to placebo due to non-compliance. We do not expect cross-over from the placebo to statin group as participants will be aware that they might be on statins already and would not want to jeopardize their safety and care. However, new clinical guidelines for prescription of statins may also influence drop-outs among participants who wish to reduce the risk of cardiovascular disease [58]. These guidelines recommend targeting men and women with cardiovascular disease, LDL cholesterol ≥ 190 mg/dL, and persons 40-75 years with diabetes or a 10-year cardiovascular disease risk $\geq 7.5\%$. Most of these people would not meet the eligibility criteria for study participation. The drop-out rate is expected to be 4 subjects in the treatment arm and 2 subjects in the placebo arm at 6 months follow-up.

13.7 Evaluation of Toxicity

All participants will be evaluable for toxicity from the time of their first dose of simvastatin.

13.8 Evaluation of Response

Changes in peak bicarbonate concentration as measured by ePFT will be evaluated for all randomized participants.

13.9 Interim Analysis

There will be no planned interim analyses.

13.10 Ancillary Studies

N/A

14. ETHICAL AND REGULATORY CONSIDERATIONS

14.1 Form FDA 1572

Prior to initiating this study, the Protocol Lead Investigator at the Lead or Participating Organization(s) will provide a signed Form FDA 1572 stating that the study will be conducted in compliance with regulations for clinical investigations and listing the investigators, at each site that will participate in the protocol. All personnel directly involved in the performance of procedures required by the protocol and the collection of data should be listed on Form FDA 1572.

14.2 Other Required Documents

14.2.1 Current (within two years) CV or biosketch for all study personnel listed on the Form FDA 1572 and Delegation of Tasks form for the Lead Organization and all Participating Organizations.

14.2.2 Current medical licenses (where applicable) for all study personnel listed on Form FDA 1572 and Delegation of Tasks form for the Lead Organization and all Participating Organizations.

14.2.3 Lab certification (*e.g.*, CLIA, CAP) and lab normal ranges for all labs listed on Form FDA 1572 for the Lead Organization and all Participating Organizations.

14.2.4 Documentation of training in “Protection of Human Research Subjects” for all study personnel listed on the FDA Form 1572 and Delegation of Tasks form for the Lead Organization and all Participating Organizations.

14.2.5 Documentation of Federalwide Assurance (FWA) number for the Lead Organization and all Participating Organizations.

14.2.6 Signed Investigator’s Brochure/Package Insert acknowledgement form

14.2.7 Delegation of Tasks form for the Lead Organization and all Participating Organizations signed by the Principal Investigator for each site and initialed by all study personnel listed on the form

14.2.8 Signed and dated NCI, DCP Financial Disclosure Form for all study personnel listed on Form FDA 1572 for the Lead Organization and all Participating Organizations

14.3 Institutional Review Board Approval

Prior to initiating the study and receiving agent, the Investigators at the Lead Organization and the Participating Organization(s) must obtain written approval to conduct the study from the appropriate IRB. Should changes to the study become necessary, protocol amendments will be submitted to the DCP PIO according to DCP Amendment Guidelines. The DCP-approved amended protocol must be approved by the IRB prior to implementation

14.4 Informed Consent

All potential study participants will be given a copy of the IRB-approved Informed Consent to review. The investigator will explain all aspects of the study in lay language and answer all questions regarding the study. If the participant decides to participate in the study, he/she will be asked to sign and date the Informed Consent document. The study agent(s) will not be released to a participant who has not signed the Informed Consent document. Subjects who refuse to participate or who withdraw from the study will be treated without prejudice.

Participants must be provided the option to allow the use of blood samples, other body fluids, and tissues obtained during testing, operative procedures, or other standard medical practices for further research purposes. If applicable, statement of this option may be included within the informed consent document or may be provided as an addendum to the consent. A Model Consent Form for Use of Tissue for Research is available through a link in the DCP website.

Prior to study initiation, the informed consent document must be reviewed and approved by NCI, DCP, the Consortium Lead Organization, and the IRB at each Organization at which the protocol will be implemented. Any subsequent changes to the informed consent must be approved by NCI, DCP, the Consortium Lead Organization’s IRB, and then submitted to each organization’s IRB for approval prior to initiation.

14.5 Submission of Regulatory Documents

All regulatory documents are collected by the Consortia Lead Organization and reviewed for completeness and accuracy. Once the Consortia Lead Organization has received complete and accurate documents from a participating organization, the Consortium Lead Organization will forward the regulatory documents to DCP’s Regulatory Contractor:

Paper Document/CD-ROM Submissions:

Regulatory Affairs Department
CCS Associates, Inc.
[name]
[name]
[contact]

E-mail Submissions:

[contact]

Regulatory documents that do not require an original signature may be sent electronically to the Consortium Lead Organization for review, which will then be electronically forwarded to DCP's Regulatory Contractor.

14.6 Other

This trial will be conducted in compliance with the protocol, Good Clinical Practice (GCP), and the applicable regulatory requirements.

APPENDIX A

Clinical Laboratory Minimum Test Requirements

Clinical labs must include at least the following tests. It is acceptable to do additional tests if they are included in the blood panels at your institution.

Blood Hematology: Complete Blood Count and Differential	Blood Chemistry: Comprehensive Metabolic Panel	Lipid Panel *	Other Blood Tests
Hemoglobin Platelet count White blood cell count (WBC, leukocytes), total Neutrophil count, absolute	Alanine aminotransferase (ALT (SGPT)) Aspartate aminotransferase (AST (SGOT)) Alkaline phosphatase (ALP) Bilirubin, total Creatinine Glucose	Total cholesterol High density lipoprotein (HDL) cholesterol Low density lipoprotein (LDL) cholesterol Triglycerides	Hemoglobin A1C (HbA1C) † Creatine phosphokinase (CPK) §

* Lipid panels will be done at Study Visits 1, 2, and 3.

† Hemoglobin A1C will be measured at Study Visits 1 and 3.

§ Creatine phosphokinase (CPK) will be measured at Study Visit 1 to establish a patient-specific reference for this indicator of muscle toxicity. If the patient reports unexplained muscle pain or weakness during the trial, CPK will be tested again to check for elevation.

